4.2 Analysis sets

The statistical analyses will be based on analysis sets defined in the following sections.

4.2.1 Intent to Treat set

All subjects that received at least one dose of VAL201 will be included. Patients enrolled for the dose escalation part of the study will be replaced if they withdraw for reasons other than a DLT associated event.

4.2.2 Per Protocol set

The per-protocol (PP) set, a subset of the ITT, will include all subjects that complete the main study (cycles 1 to 6). Subjects that do not complete the main study and subjects with major protocol deviations that may affect the data will be excluded from the PP set.

The classification of major and minor protocol deviations and the resulting definition of analysis sets will be performed prior to the analysis and will be approved by the Sponsor. The determination of protocol deviations and their assessment will be fixed in the evaluability plan.

A summary of the number of subjects per analysis set will be given and reasons for exclusion of a subject from an analysis set will be listed in the evaluability listing.

4.2.3 Safety set

The safety set will include all patients that have been given at least one dose by subcutaneous (s.c.) injection of VAL201.

Forms				
Title		Statistical Analysis Plan Template		
Code		Version	Effective Date	Page
FRM_ST03_032		01	23 Apr 2015	14 of 24

4.2.4 PK set

The PK set will include all subjects in the safety set with evaluable PK data (i.e.: all patients with a calculated concentration available).

4.3 Sub-group analyses

NA.

4.4 Handling of missing and incomplete data

Missing values will be included in the denominator count when computing percentages. Only the non-missing values will be evaluated for computing summary statistics. AEs that have missing onset dates will be considered to be treatment-emergent, unless the stop date is known to be prior to the first administration of VAL201.

In order to calculate the duration of tumor, the following rules will be applied for partial dates of histological/cytological diagnosis:

- if only the day is missing, the 15th of the month will be assumed;
- if the day and the month are missing, 30th June will be assumed.

4.5 Derived Variables

Age

Subject age (in years) will be captured on the CRF at the Screening (day -28 to 0).

Body Mass Index (BMI) (kg/m²)

BMI will be calculated at Screening using the following formula:

$$\text{BMI} = \frac{\text{Body weight (kg)}}{(\text{height (cm})/100)^2}$$

Duration of tumour (years)

Duration of tumour will be calculated using the following formula:

Duration of tumour = (Informed Consent signature date - Date of histological/cytological diagnosis +1)/365.25

Responder subject (for response rate calculation) – prostate cancer subjects only

A subject is defined responder if completed 6 treatment cycles without being labelled as having disease progression by PCWG2 criteria in any cycle, i.e. if all the 4 PCWG2 Evaluation questions, included in the TUMOR ASSESSMENT – PROSTATE/ PCWG2 EVALUATION CRF Form, are answered as “No” this indicate no progression for the subject.

Forms				
Title		Statistical Analysis Plan Template		
Code		Version	Effective Date	Page
FRM_ST03_032		01	23 Apr 2015	15 of 24

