5.12 Tumour assessment prostate

Tumour assessment for prostate cancer patients will follow the PCWG2 guidelines or RECIST 1.1 guidelines and may include assessment of serum prostate-specific antigen (PSA) at screening and every 3 weeks or at the end of every cycle.

Forms				
Title		Statistical Analysis Plan Template		
Code		Version	Effective Date	Page
FRM_ST03_032		01	23 Apr 2015	19 of 24

A summary table for tumour assessment at screening and at each applicable cycle will be produced presenting descriptive statistics for longest tumour diameter (mm) reported as well as duration of tumour (years) and method of examination; longest tumour diameter will be classified by tumour location and such categories will be defined by a study medical expert reviewing the related information collected.

The assessment of prostate-specific antigen PSA outcomes will be summarised for each patient and time point including the percent change in PSA from baseline to tumour assessment time point.

An estimate of pre-treatment PSA doubling time will be presented in a summary table together with descriptive statistics for PSA values at each cycle and the related percent change from baseline.

Baseline PSA value is defined as the last available assessment before treatment start (which will be actually the PSA value collected at Cycle 1 Day 1).

Thereafter tumour assessment and prostate-specific antigen PSA assessment results will be listed, including also maximum decline in PSA during study.

If other methods were used to assess the tumour such CT scan or MRI then the results of the tests will be listed for each patient by time point.

6. Evaluation of objectives

The evaluation of the primary objective will be based on the safety set, the evaluation of the secondary objective will be based on the ITT set and the evaluation of the exploratory objective will be based on the ITT set and the PP set separately. Tables and listings will be presented separately.

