6.2.3 Evaluation of anti-tumour activity of VAL201

For patients with prostate cancer or other tumour types where applicable, response rate (assessed by PCWG2 for prostate cancer or RECIST 1.1 for other tumour types), was planned to include CT (or MRI), radionuclide bone scan, and PSA at the selected dose level and assessed in a 2 stage analysis

Forms				
Title		Statistical Analysis Plan Template		
Code		Version	Effective Date	Page
FRM_ST03_032		01	23 Apr 2015	21 of 24

(dose escalation and enrichment respectively). Stage 2 was not reached within the study and only prostate cancer patients were finally included in the trial, so response rate will be summarized for Dose Escalation Stage only, based on responder definition reported in section 4.5; exact 95% CI will be calculated. Prostate Specific Antigen assessment will be summarized as indicated in section 5.12 of this SAP.

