7.2 Tables listings and figures

7.2.1 Tables:

 cros nt	Forms			
	Title	Statistical Analysis Plan Template		
	Code	Version	Effective Date	Page
	FRM_ST03_032	01	23 Apr 2015	22 of 24

TABLE 14.1-1	DISPOSITION OF PATIENTS / SUMMARY OF ALL PATIENTS AND ANALYSIS SET
TABLE 14.1-2.1	SUMMARY OF MAJOR PROTOCOL DEVIATION / INTENT TO TREAT POPULATION
TABLE 14.1-2.2	SUMMARY OF MINOR PROTOCOL DEVIATION / INTENT TO TREAT POPULATION
TABLE 14.1-3.1	DEMOGRAPHIC CHARACTERISTIC / INTENT TO TREAT POPULATION
TABLE 14.1-4	SUMMARY OF TUMOUR ASSESSMENT / INTENT TO TREAT POPULATION
TABLE 14.1-5.1	MEDICAL HISTORY BY SYSTEM ORGAN CLASS AND PREFERRED TERM / INTENT TO TREAT POPULATION
TABLE 14.1-5.2	CONCOMITANT DISEASE BY SYSTEM ORGAN CLASS AND PREFERRED TERM / INTENT TO TREAT POPULATION
TABLE 14.1-6.1	PREVIOUS MEDICATIONS / INTENT TO TREAT POPULATION
TABLE 14.1-6.2	CONCOMITANT MEDICATIONS / INTENT TO TREAT POPULATION
TABLE 14.2-1	SUMMARY OF DOSE LIMITING TOXICITY (DLT) BY COHORT / SAFETY POPULATION
TABLE 14.2-3.1	PROSTATE SPECIFIC ANTIGEN (PSA) ASSESSMENT / INTENT TO TREAT POPULATION
TABLE 14.2-3.2	PROSTATE SPECIFIC ANTIGEN (PSA) ASSESSMENT / PER PROTOCOL POPULATION
TABLE T14.2-4.1	SUMMARY OF RESPONSE RATE ANTI TUMOUR ACTIVITY / INENT TO TREAT POPULATION
TABLE T14.2-4.2	SUMMARY OF RESPONSE RATE ANTI TUMOUR ACTIVITY / PER PROTOCOL POPULATION
TABLE T14.3.1-1.1	SUMMARY OF TREATMENT-EMERGENT ADVERSE EVENTS BY DOSE/ DOSE ESCALATION SAFETY POPULATION
TABLE T14.3.1-2.1	SUMMARY OF TREATMENT EMERGENT ADVERSE EVENT BY SYSTEM ORGAN CLASS AND BY DOSE / DOSE ESCALATION SAFETY POPULATION
TABLE T14.3.1-3.1	SUMMARY OF TREATMENT EMERGENT ADVERSE EVENT BY SYSTEM ORGAN CLASS AND BY SEVERITY / DOSE ESCALATION SAFETY POPULATION
TABLE T14.3.1-4.1	SUMMARY OF TREATMENT EMERGENT ADVERSE EVENT BY SYSTEM ORGAN CLASS AND BY CAUSALITY / DOSE ESCALATION SAFETY POPULATION
TABLE 14.3.4-1.1	ESTERN CO-OPERATIVE ONCOLOGY GROUP (ECOG) PERFORMANCE STATUS / INTENT TO TREAT POPULATION
TABLE 14.3.4-1.2	ESTERN CO-OPERATIVE ONCOLOGY GROUP (ECOG) PERFORMANCE STATUS / PER PROTOCOL POPULATION
TABLE 14.3.4-2.1	SUMMARY VITAL SIGNS BY CYCLE AND VISIT / INTENT TO TREAT POPULATION

 cros nt	Forms			
	Title	Statistical Analysis Plan Template		
	Code	Version	Effective Date	Page
	FRM_ST03_032	01	23 Apr 2015	23 of 24

TABLE 14.3.4-2.2	SUMMARY VITAL SIGNS BY CYCLE AND VISIT / PER PROTOCOL POPULATION
TABLE 14.3.4-3.1.1	LABORATORY PARAMETERS: CLINICAL CHEMISTRY BY CYCLE AND TIME POINTS / INTENT TO TREAT POPULATION

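### Completing six cycles is both part of the responder definition and the entry condition of the PP set, so before deviation exclusions the PP response rate cannot fall below the ITT rate; Section 6 does not call for that table, and the response is only non-progression

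*SAP*

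**What the plan says.** Section 4.5 of the SAP defines the endpoint: "A subject is defined responder if completed 6 treatment cycles without being labelled as having disease progression by PCWG2 criteria in any cycle". It adds that if all four PCWG2 questions on the CRF form are answered No, "this indicate no progression for the subject".

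Section 4.2.2 says that the PP set "will include all subjects that complete the main study (cycles 1 to 6"), and that non-completers are left out. It also says that "subjects with major protocol deviations that may affect the data will be excluded from the PP set". For the ITT set, Section 4.2.1 says: "All subjects that received at least one dose of VAL201 will be included".

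Section 2.1.2 lists anti-tumour activity as a secondary objective. Section 6 says that "the evaluation of the secondary objective will be based on the ITT set" and mentions the PP set only for the exploratory objective. Section 6.2.3 says that "response rate will be summarized for Dose Escalation Stage only, based on responder definition reported in section 4.5", with an exact 95% CI; it names no PP analysis.

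Section 7.2.1 nevertheless lists two response tables: T14.2-4.1 on the ITT set, and T14.2-4.2, titled "SUMMARY OF RESPONSE RATE ANTI TUMOUR ACTIVITY / PER PROTOCOL POPULATION".

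**The concern.** A PP analysis is usually read as a sensitivity check on the ITT result. It cannot serve that purpose when entry to the PP set is itself part of the outcome. Here every responder has completed six cycles by definition, and every patient who stopped early is a failure. Restricting to completers removes failures only. The result is a second rate, equal to or higher than the first, that looks like support for activity but owes any excess to the choice of denominator. The selection acts on one component of the outcome only: a completer who has progressed stays in the PP set as a non-responder.

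Two further points add to this. The table departs from Section 6, which assigns this objective to the ITT set. And the label, response rate and anti-tumour activity, suggests shrinkage or PSA decline, although the definition asks only for absence of progression. In a single-arm study, that cannot separate a drug effect from slowly progressing disease.

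**Working it through.** The SAP states no response rate, target or power for this endpoint, so there is no figure of its own to reproduce. The check is one of set logic, followed by illustrations on assumed counts.

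**Inputs.**
- N = treated patients (ITT, Section 4.2.1).
- C = patients completing cycles 1 to 6 (PP entry, Section 4.2.2, before deviation exclusions).
- R = responders (Section 4.5).
- Section 4.4 keeps missing values in percentage denominators, so early stoppers remain in the ITT denominator.

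**Relation between the two rates.** Responders are a subset of completers, and completers are a subset of the treated, so R ≤ C ≤ N. Then:

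- ITT rate = R/N
- PP rate = R/C = (R/N) × (N/C) ≥ R/N

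Equality holds only if C = N or R = 0. Enumerating every combination with N from 1 to 42 (42 is the maximum enrolment) and C at least 1 gave 14,147 cases: none with a PP rate below the ITT rate, 1,806 equal, and the rest higher.

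**Size of the multiplier N/C (completion fractions assumed).**

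| Completion C/N | N/C |
|---|---|
| 100% | 1 |
| 67% | 1/0.67 = 1.5 |
| 50% | 1/0.50 = 2 |
| 33% | 1/0.33 = 3 |

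**Example with exact (Clopper-Pearson) 95% CIs, assuming N = 12 and R = 3.**

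| Set | Rate | 95% CI |
|---|---|---|
| ITT | 3/12 = 25% | 5.5% to 57.2% |
| PP, 8 completers | 3/8 = 37.5% | 8.5% to 75.5% |
| PP, 4 completers | 3/4 = 75% | 19.4% to 99.4% |

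The same three responders give 25%, 37.5% or 75%, depending only on how many non-responders completed six cycles.

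**What happens if the PP interval is read as applying to all treated patients.** Assume 12 treated patients, independent completion with the stated probability, and 75% of completers free of progression. The true all-treated rate is then completion × 0.75. Exact enumeration gives the probability that each 95% CI excludes that rate:

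| Completion | True all-treated rate | PP CI misses | ITT CI misses |
|---|---|---|---|
| 67% | 50% | 17.6% | 3.9% |
| 50% | 37.5% | 29.8% | 1.3% |
| 33% | 25% | 39.4% | 1.4% |

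**Effect of deviation exclusions.** Removing responders for major deviations can offset or reverse the order.
- N = 12, C = 10, R = 6, two responders excluded: ITT 6/12 = 50%; PP (6 − 2)/(10 − 2) = 4/8 = 50%.
- N = 12, C = 8, R = 4, three responders excluded: ITT 4/12 = 33.3%; PP 1/5 = 20%.

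**What the endpoint measures.** Section 3.1 sets six cycles of 21 days: 6 × 21 = 126 days. Four No answers establish absence of progression. Nothing in Section 4.5 requires a PSA fall or a reduction in lesion size.

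**The case against.** The strongest reply is about weight. The primary objective is the MTD/MAD on the safety set, response is purely descriptive, the study closed early, and the ITT table is planned and correct. The PP table names its population, and Section 4.2.2 provides for reporting set sizes and reasons for exclusion, so a reader can see the denominator change. All of this stands, and it confines the harm to reporting. It does not make the PP figure informative about activity.

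Second, the PP interval is valid for what it estimates: under the assumptions above it misses the completers' own rate of 75% only about 1% of the time. That is right. The coverage table shows the cost of reading the interval as a statement about treated patients; it does not show that the interval is wrongly computed.

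Third, Section 6 does not expressly forbid supplementary PP displays, and other PP tables, such as PSA in T14.2-3.2, also fall outside it, so deleting one table leaves a wider mismatch. The mismatch is real, but those tables do not define success by completing six cycles and so lack this built-in selection. A footnote marking T14.2-4.2 as completers only would be a milder remedy, but it would keep an estimate that no objective calls for.

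Fourth, the inequality depends on completion being enforced. If the clause about four No answers were programmed alone, a patient who stopped early without progression could count as a responder, and the ordering would no longer be guaranteed. The plain wording requires completion; the possible second reading is a reason to state the rule explicitly.

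Finally, Section 4.5 discloses the definition, and renaming could diverge from protocol terminology that is not available here. The disclosure helps a reader of the SAP, but not someone who sees only the table title.

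**Conclusion.** The concern holds and should be fixed; it is a reporting matter, not one that threatens the study's conclusions on dose. On the plain wording of Sections 4.5 and 4.2.2, and before deviation exclusions, the PP rate is the ITT rate multiplied by N/C and can never be lower. There is no inflation if everyone completes or no one responds. How large it would be in this study cannot be read from the SAP, since all completer and responder counts used above are assumed, and deviation exclusions could offset it. Two parts need no assumption: T14.2-4.2 has no basis in Section 6, and the quantity called a response rate is non-progression through six cycles.

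**What to change.** - Drop Table T14.2-4.2. Report the rate with its exact 95% CI on the ITT set only (T14.2-4.1), as Section 6 already specifies.
- Add to Section 6.2.3: *All treated subjects are in the denominator; subjects who stop before completing 6 cycles count as not meeting the endpoint.* This follows from Sections 4.2.1, 4.4 and 4.5 read together, but stating it once removes the alternative reading of the four-question clause.
- Rename the endpoint *rate of completing 6 cycles without PCWG2 progression* in Sections 4.5 and 6.2.3 and in the title of T14.2-4.1, and align the wording in Sections 3.4 and 4.1. Check the new name against the protocol's terminology.
- Leave the PP set definition and the other PP tables as they are.

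The cost is SAP wording and one table fewer, with no new data or programming. What is given up is the PP view of this endpoint, and the remaining figure and label will look less favourable.

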4.6 Changes in the planned analysis

The SAP has been updated due to changes in the study design (see Protocol Amendment Version 5 and 6). The main changes are:

- Cohort 5 will start treatment on a dose of 8mg/kg (rather than 5mg/kg). Moreover, from cycle 4 day 1 onwards, the dose may change.
- The schedule for the following parameters has changed: vital signs, tumor assessment, and pharmacokinetics.
- For each cohort, patients will be followed up for DLT not only during the first cycle, but during each cycle.

Furthermore, due to the premature closure of the study, the analysis on enrichment phase will not be produced. This phase was not reached within the study.

Any assessments available on Final cycle 6 day 22/cycle 7 day1, will be included in the planned summary tables by cycle produced on the main study phase.

The following exploratory endpoints will also not be analyzed, as per Sponsor decision:

- Assessment of additional pharmacodynamics activity of VAL201. PD assessment is limited to only those parameters contained within Clinical Chemistry (Testosterone, LH, PSA).
- Assessment of tumour biomarkers.

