t _{max}	time to reach maximum concentration
V _{ss}	the apparent volume of distribution at steady state calculated as: Dose/AUC x (AUMC/ AUC _{0-∞} - T/2) where T is the duration of intravenous injection
λ _z	the apparent terminal rate constant, estimated using the negative slope of the least square regression analysis of the log concentration versus time data for the terminal linear portion of the curve

Revision History

Document Version	Changes Made	Document Date
Draft 1	Draft specification based on the following documents: 
 • Study protocol VAL201-001 F2.0 • VAL201-001 CRF 	24 AUG 2015
Draft 2	Updated draft after amendment	08 JUL 2016
Final	Updated after Sponsor comments	24 AUG 2016
Amendment Draft 1.0	Updates following protocol amendment VAL201-001 version F5.0	29 JAN 2018
Amendment Draft 2.0	Updates following protocol amendment VAL201-001 version F6.0	17 JUN 2019
Amendment Final 2.0	Finalized Amendment version after Sponsor confirmation	05 SEP 2019
Amendment Draft 2.1	Updates following early study termination decision	10 FEB 2020
Amendment Draft 2.2	Updates following discussion with Sponsor	11 JUN 2020
Amendment Final 3.0	Finalized Amendment version after Sponsor confirmation	17 JUL 2020

Forms				
Title		Statistical Analysis Plan Template		
Code		Version	Effective Date	Page
FRM_ST03_032		01	23 Apr 2015	7 of 24

1. Introduction

The present Statistical Analysis Plan (SAP) outlines analysis to guide the programming for the data analyses of clinical study VAL201-001 protocol version F6.0 (last version - 7.0 - of study protocol was finalized and approved but never implemented for use in the study). The study was closed to further recruitment in January 2020 due to difficulty in recruiting patients to meet the inclusion/exclusion criteria within the current protocol; the treatment paradigm for patients had significantly evolved during the five years of patient recruitment being open. Any changes to the study protocol or Case Report Form (CRF) may necessitate updates to the SAP. In case of deviations from the finalized SAP, explanations will be provided in the clinical study report.

Relevant applicable CROS NT Standard Operating Procedures (SOP) will be followed in compliance with the agreement with the Client.

2. Study Objectives

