3.1 General design and plan

This clinical study is designed to establish the MTD/MAD, safety, tolerability and PK of VAL201 by testing the drug (VAL201) on patients with incurable, locally advanced or metastatic prostate cancer and other advanced solid tumors. The design is a Phase I/II, open-label single-arm dose escalation study. The study design consists of a dose escalation part followed by an enrichment part. The study features includes: five cohorts of up to six patients, six cycles (main study) each cycle will last 21 days and an extended treatment period of VAL201 if a patient is considered suitable. Events that occur during each cycle will be considered for Dose Limiting Toxicity (DLT) assessment and therefore to establish the MTD/MAD.

The dose escalation will follow an accelerated enrolment of 3+3 design where the first two cohorts will enroll 1 patient each with an accelerated dose escalation schedule as described on Section 4.2 of the clinical study protocol (VAL201-001 version F6.0). Each patient will be followed up for AEs and DLT during each cycle. Where the Cohort Review Committee (CRC) suspects that drug-related events have occurred that merit further exploration at that dose level, they will request that the cohort 1 or 2 must enroll 3 more patients in order to thoroughly evaluate safety events prior to escalation. Cohorts of 3 patients will be enrolled from the 3rd cohort onwards (or earlier where the CRC recommend due to safety data evaluation). After a DLT has been identified the cohort will be expanded to 6 patients. If a second DLT is reported this will be declared the MTD.

The starting dose of VAL201 for the first cohort of patients will be 0.5 mg/kg/dose given on Days 1, 8 and 15 of each cycle. In the absence of DLT, the dose of VAL201 will be escalated for future cohorts in recommended increments according to the rules for dose escalation as described in Section 4.2 of clinical study protocol. All dose escalation decisions will be made by a CRC who shall convene to review all available safety data.

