3.5 Safety endpoints

The safety analysis will include all patients screened and enrolled for whom has been given at least one dose by subcutaneous (s.c.) injection of VAL201.

The number and percent of subjects experiencing Adverse Events (AEs) will be reported by dose. In addition the incidence of AE and suspected DLTs will be graded according to the Common Terminology Criteria for AEs (CTCAE), version 4.03.

In order to assess the primary objective of the analysis the following classification of the safety variables will be apply:

Forms				
Title		Statistical Analysis Plan Template		
Code		Version	Effective Date	Page
FRM_ST03_032		01	23 Apr 2015	12 of 24

Dose Limiting Toxicity (DLT)

A DLT is defined as a drug –related Grade 3 or 4 AE (from CTCAE version 4.03) that, in the opinion of the Investigator and/or CRC, represents a clinically significant hazard to the patient; a list of exceptions is presented in Section 4.2.1 of the study protocol.

DLT events will also be considered in terms of:

- inability to administer the planned Cycle 1 dose administration schedule;
- clinically significant toxicity events considered related to VAL201 which lead to a dose delay of more than 7 days during Cycle 1.

Pre-treatment adverse events-

An AE will be classified as pre-treatment AE if it starts before the date/time of day of first medication intake in the study.

Treatment-emergent adverse event (TEAE)

An AE will be classified as a TEAE if it starts on or after the date/time of day 1 cycle 1 of the study. In case of missing or incomplete dates/times not allowing a direct allocation to any of the two categories of AEs, it will be considered to be treatment-emergent, unless the stop date is known to be prior to the first administration of the study medication. The AE will be allocated to the first category allowed by the available data, according to the following order:

- TEAE
- Pre-treatment.

Serious adverse event (SAE)

A SAE is an AE judged as serious.

Adverse Event Related to study drug

An AE is considered as related to study drug if it is judged as “Possibly Related”, “Probably Related” or “Definitely Related” or with missing relationship.

Adverse event leading to death

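### DLT follow-up was widened mid-study from Cycle 1 to every cycle, so the single by-cohort DLT table may compare cohorts over unequal windows

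*SAP*

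**What the plan says.** Section 4.6 opens with "The SAP has been updated due to changes in the study design (see Protocol Amendment Version 5 and 6" and a closing bracket, then lists the main changes. One reads "For each cohort, patients will be followed up for DLT not only during the first cycle, but during each cycle". Another reads "Cohort 5 will start treatment on a dose of 8mg/kg (rather than 5mg/kg", again with a closing bracket. The SAP does not say which of the two amendments changed the DLT window.

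The current design text in section 3.1 uses the wider window without singling out a cohort: "Events that occur during each cycle will be considered for Dose Limiting Toxicity (DLT) assessment". Section 6.1 does the same.

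Section 3.5 defines a DLT as a drug-related Grade 3 or 4 event "that, in the opinion of the Investigator and/or CRC, represents a clinically significant hazard to the patient". It adds two further criteria, both confined to Cycle 1: not being able to give the planned Cycle 1 doses, and a related toxicity that delays dosing by over a week in that cycle.

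For reporting, section 7.2.1 plans one table, 14.2-1, titled "SUMMARY OF DOSE LIMITING TOXICITY (DLT) BY COHORT / SAFETY POPULATION". Section 6.1 also promises DLTs by dose level and as a listing, but section 7.2.2 names no DLT listing. No output is split by cycle, by DLT window or by protocol version.

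**The concern.** In an escalation study, calendar time and dose rise together. If the DLT window lengthens part-way, the later, higher-dose cohorts are watched for DLTs over more cycles than the earlier ones. Equal true toxicity would then give more recorded DLTs at the higher doses, and the lower doses would look cleaner than they were shown to be.

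Saying that the wider window holds for each cohort does not settle this. A DLT cannot be read off from grade and causality alone, because someone must have judged the event a hazard. For patients treated while only Cycle 1 counted, nobody may have been asked that question about Cycles 2 to 6. The SAP neither says that those events were judged later nor separates the affected patients.

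At stake is how far the DLT counts by cohort, which are the main display for the primary objective, can be read across doses.

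**Working it through.** **Was there a change, and when?** The wording in section 4.6 means that the previous window was Cycle 1 only. Section 1 says recruitment closed in January 2020 after about five years, so it opened around early 2015. In the Revision History, the entry "Updates following protocol amendment VAL201-001 version F5.0" is dated 29 January 2018, about three years into recruitment; the entry for F6.0 is dated 17 June 2019. These are dates of SAP updates, not of the amendments or of enrolment. Section 4.6 sets the starting dose of Cohort 5 in the future tense, and cohorts follow one another. That earlier cohorts were treated at least partly under the Cycle 1 window is therefore very probable but not documented.

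**The SAP's own figures.** The SAP gives no figure for DLT ascertainment. Its only computable design figure is the 3+3 table in section 3.3. With true DLT rate p, P(escalate) = (1−p)^3 + 3p(1−p)^2 × (1−p)^3. At p = 20, 30, 40, 50 and 60% this gives 70.9, 49.4, 30.9, 17.2 and 8.2%, against the stated 71, 49, 31, 17 and 8%. The table reproduces.

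**Nominal windows.** Section 3.1 gives "six cycles (main study) each cycle will last 21 days". Six cycles are 6 × 21 = 126 days and one cycle is 21 days, so the ratio is 126/21 = 6. Only a patient who completes all six cycles reaches it within the main study. Section 3.1 also allows extended treatment, so six cycles is not a strict ceiling. In Cohort 5, section 3.1 allows escalation at Cycle 4, which leaves three cycles (63 days, ratio 3) at the starting dose.

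**Chance of a counted DLT.** The per-cycle DLT risk h is an assumption, as the SAP gives none. With constant h, the chance of at least one DLT in six cycles is 1 − (1−h)^6, against h in Cycle 1 alone. For three patients with per-patient probability P, the chance of at least one DLT is 1 − (1−P)^3.

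| Assumed h per cycle | Cycle 1 only | Six cycles | Ratio | At least one DLT in 3 patients: Cycle 1 only / six cycles |
|---|---|---|---|---|
| 2% | 2% | 11.4% | 5.7 | 5.9% / 30.5% |
| 5% | 5% | 26.5% | 5.3 | 14.3% / 60.3% |
| 10% | 10% | 46.9% | 4.7 | 27.1% / 85.0% |
| 20% | 20% | 73.8% | 3.7 | 48.8% / 98.2% |
| 30% | 30% | 88.2% | 2.9 | 65.7% / 99.8% |

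If instead the risk halves with each cycle, starting values of 5, 10 and 20% give six-cycle probabilities of 9.5, 18.4 and 34.6%, and ratios of 1.9, 1.8 and 1.7.

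All these figures assume that patients complete six cycles and that pre-amendment patients were judged in Cycle 1 only. The two criteria tied to Cycle 1 add no difference between cohorts.

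**The case against.** The strongest reply is that unequal ascertainment is not documented. Sections 3.1, 4.6 and 6.1 all apply the every-cycle window without exempting a cohort, and section 6.2.1 has adverse events evaluated in every cycle and in follow-up for all patients. On that reading there is one window and the data to fill it. Whether later-cycle events in early patients were judged would be found in committee records or the CRF, which are not at hand. This stands in part: unequal windows can be called probable, not established. It does not remove the gap, because recorded events still need a judgement and the SAP does not say that it was made.

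Three further replies stand:

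- The factor of 6 compares nominal windows; it is not a ratio of DLT counts.
- The MAD is the highest dose given (section 2.1.1), so no DLT count can move it.
- The DLT analysis is descriptive, and treatment-emergent events are tabulated by dose, severity and causality and listed individually, so a later-cycle event in an early cohort remains visible whatever its DLT label.

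A reader might go further and infer that escalation decisions were distorted, by putting a six-cycle risk into the 0-of-3 or 1-of-6 rule. At 5% per cycle that would give 97% against 57%. The SAP does not support this use: section 6.1 places the committee's escalation review at the end of Cycle 1, so the pair does not describe the decisions.

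**Conclusion.** The point holds as a question of comparability. The SAP records a mid-study widening of the DLT window, does not say how it applies to patients already treated, and plans one by-cohort table with no count over a common window. Followed as written, the table may set unlike counts side by side, with the difference running in the same direction as dose.

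The size depends on assumptions outside the SAP. If early patients were judged in Cycle 1 only and later patients completed six cycles, the chance of a counted DLT differs by about 3 to 6 times under constant per-cycle risk of 30% to 2%, and by less than 2 times under risk that halves each cycle.

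A reader might infer that the later cohorts did in fact have six times the DLT ascertainment, or that the MTD/MAD is biased as a result. The SAP shows neither: the timing is inferred, any retrospective judgement is unknown, the MAD is unaffected, and the underlying events would still appear in the treatment-emergent listings. The change is worth making before the tables are produced because it costs little and bears on the primary objective.

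**What to change.** In section 6.1 and Table 14.2-1:

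- Report DLTs in Cycle 1 separately from DLTs in Cycle 2 onward. Cycle 1 is the window common to all cohorts and the one available at the end-of-Cycle-1 review.
- For the later DLTs, show the number of cycles at risk and the dose at onset. The dose matters most in Cohort 5, where it may change at Cycle 4.
- State that comparison across cohorts rests on the Cycle 1 count.
- Footnote which DLT window each patient was followed under, and whether later-cycle events in pre-amendment patients were judged against the DLT definition. Mark any such review as retrospective, since it would be made with the outcome known.

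The cost is some SAP wording, an extra column or two and a footnote. The adverse event data needed are already collected.
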